### Follow-up of AEs and SAEs

- The investigator is obligated to perform or arrange for the conduct of supplemental measurements and/or evaluations as medically indicated or as requested by a UCB representative to elucidate the nature and/or causality of the AE or SAE as fully as possible. This may include additional laboratory tests or investigations, histopathological examinations, or consultation with other health care professionals.
- An AE should be followed until it has resolved, has a stable sequelae, the investigator determines that it is no longer clinically significant, or the participant is lost to follow-up. This follow-up requirement applies to AEs, SAEs, and AEs of special interest.
- New or updated information will be recorded in the originally completed eCRF.
- The investigator will submit any updated SAE data to UCB within 24 hours of receipt of the information.

## Reporting of SAEs

### SAE Reporting to UCB via an Electronic Data Collection Tool

- The primary mechanism for reporting an SAE to UCB will be the electronic data collection tool.
- If the electronic system is unavailable for more than 24 hours, then the site will use the paper SAE data collection tool (see next section).
- The site will enter the SAE data into the electronic system as soon as it becomes available.
- After the study is completed at a given site, the electronic data collection tool will be taken off-line to prevent the entry of new data or changes to existing data.
- If a site receives a report of a new SAE from a study participant or receives updated data on a previously reported SAE after the electronic data collection tool has been taken off-line, then the site can report this information on a paper SAE form (see next section) or to the study physician or medically qualified designee by telephone.
- Contacts for SAE reporting can be found on page 3.

### SAE Reporting to UCB via Paper CRF

- Facsimile transmission of the SAE paper CRF is the preferred method to transmit this information to the UCB.
- In rare circumstances and in the absence of facsimile equipment, notification by telephone is acceptable with a copy of the SAE data collection tool sent by overnight mail or courier service.
- Initial notification via telephone does not replace the need for the investigator to complete and sign the SAE CRF pages within the designated reporting time frames.
- Contacts for SAE reporting can be found on page 3.

## 11.4 Appendix 4: Contraceptive Guidance and Collection of Pregnancy Information

### Definitions

#### Woman of Childbearing Potential

A woman is considered fertile following menarche and until becoming post-menopausal unless permanently sterile (see below).

Women in the following categories **are not considered women of childbearing potential**:

1. Premenarchal
2. Premenopausal female with 1 of the following:
  - Documented hysterectomy
  - Documented bilateral salpingectomy
  - Documented bilateral oophorectomy
3. Postmenopausal female
  - A postmenopausal state is defined as no menses for 12 months without an alternative medical cause. A high follicle stimulating hormone (FSH) level in the postmenopausal range may be used to confirm a postmenopausal state in women not using hormonal contraception or hormonal replacement therapy (HRT). However, in the absence of 12 months of amenorrhea, a single FSH measurement is insufficient.
  - Females on HRT and whose menopausal status is in doubt will be required to use one of the non-estrogen hormonal highly effective contraception methods if they wish to continue their HRT during the study. Otherwise, they must discontinue HRT to allow confirmation of postmenopausal status before study enrollment.

### Contraception Guidance

#### Male participants

Male participants with female partners of childbearing potential are eligible to participate if they agree to ONE of the following during this study:

- Are abstinent from penile-vaginal intercourse as their usual and preferred lifestyle (abstinent on a long term and persistent basis) and agree to remain abstinent.
- Agree to use a male condom plus partner use of a contraceptive method with a failure rate of <1% per year as described in the table below when having penile-vaginal intercourse with a woman of childbearing potential who is not currently pregnant.

In addition, male participants must refrain from donating sperm for the duration of the study and after the final dose of study medication as follows:

1. For 3 months if participating in Part A or Part A1 of the study;
2. For 6 months if participating in Part B or Part C of the study.

Male participants with a pregnant or breastfeeding partner must agree to remain abstinent from penile-vaginal intercourse or use a male condom during each episode of penile penetration for the duration of the study and, after the final dose of study medication as follows:

1. For 3 months if participating in Part A or Part A1 of the study;
2. For 6 months if participating in Part B or Part C of the study.

### **Female participants**

Female participants of childbearing potential are eligible to participate if they agree to use a highly effective method of contraception consistently and correctly as described in the table below.

It is currently unknown whether trifluridine/tipiracil (Lonsurf®) may reduce the effectiveness of hormonal contraceptives, and therefore women using hormonal contraceptives should add a barrier contraceptive method.

### **Highly Effective Contraceptive Methods**

Highly Effective Contraceptive Methods That Are User Dependenta
Failure rate of <1% per year when used consistently and correctly.
Combined (estrogen and progestogen containing) hormonal contraception associated with inhibition of ovulation a 

• Oral

• Intravaginal

• Transdermal

Progestogen only hormonal contraception associated with inhibition of ovulation 

• Oral

• Injectable

Highly Effective Methods That Are User Independentb
Implantable progestogen only hormonal contraception associated with inhibition of ovulation 

• Intrauterine device (IUD)

• Intrauterine hormone-releasing system (IUS)

• Bilateral tubal occlusion

Vasectomized partner
A vasectomized partner is a highly effective contraception method provided that the partner is the sole male sexual partner of the woman of childbearing potential and the absence of sperm has been confirmed. If not, an additional highly effective method of contraception should be used.
Sexual abstinence
Sexual abstinence is considered a highly effective method only if defined as refraining from heterosexual intercourse during the entire period of risk associated with the study medication. The reliability of sexual

abstinence needs to be evaluated in relation to the duration of the study and the preferred and usual lifestyle of the participant.

**NOTES:**

- a) Typical use failure rates may differ from those when used consistently and correctly. Use should be consistent with local regulations regarding the use of contraceptive methods for participants participating in clinical studies.
- b) Hormonal contraception may be susceptible to interaction with the study medication, which may reduce the efficacy of the contraceptive method. In this case, 2 highly effective methods of contraception should be utilized during the treatment period and after the final dose of study medication, as follows:
  1. For at least 3 months if participating in Part A or Part A1 of the study;
  2. For at least 6 months if participating in Part B or Part C of the study.

**Pregnancy testing**

- Women of childbearing potential should only be included after a confirmed menstrual period and a negative highly sensitive serum pregnancy test.
- Additional pregnancy testing should be performed at each visit during the treatment period and within 30 days after the final dose of study medication and as required locally.
- Pregnancy testing will be performed whenever a menstrual cycle is missed or when pregnancy is otherwise suspected.
- Pregnancy testing, with a sensitivity of at least 25mIU/mL will be performed.

**Male participants with partners who become pregnant**

- The investigator will attempt to collect pregnancy information on any male participant's female partner who becomes pregnant while the male participant is in this study. This applies only to male participants who receive study medication.
- After obtaining the necessary signed informed consent from the pregnant female partner directly, the investigator will record pregnancy information on the appropriate form and submit it to the Sponsor within 24 hours of learning of the partner's pregnancy. The female partner will also be followed to determine the outcome of the pregnancy. Information on the status of the mother and child will be forwarded to the Sponsor. Generally, the follow-up will be at least 12 months after the delivery date. Any termination of the pregnancy will be reported regardless of fetal status (presence or absence of anomalies) or indication for the procedure.

**Female participants who become pregnant**

- Any female participant who becomes pregnant while participating in the study will discontinue study medication or be withdrawn from the study OR may request continuation of study medication.
- The investigator will collect pregnancy information on any female participant who becomes pregnant while participating in this study. Information will be recorded on the appropriate form and submitted to the Sponsor within 24 hours of learning of a participant's pregnancy. The participant will be followed to determine the outcome of the pregnancy. The investigator will collect follow-up information on the participant and the neonate, and the information will be forwarded to the Sponsor. Generally, the follow-up will be at least 12 months after

the delivery date. Any termination of pregnancy will be reported, regardless of fetal status (presence or absence of anomalies) or indication for the procedure.

- While pregnancy itself is not considered to be an AE or SAE, any pregnancy complication or elective termination of a pregnancy will be reported as an AE or SAE. A spontaneous abortion is always considered to be an SAE and will be reported as such. Any post-study pregnancy related SAE considered reasonably related to the study medication by the investigator will be reported to the Sponsor as described in Section 9.2.5. While the investigator is not obligated to actively seek this information in former study participants, he or she may learn of an SAE through spontaneous reporting.

This document cannot be used to support any marketing application and any extensions or variations thereof.  
PUBLIC COPY

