### **Treatment groups and duration**

[figure not shown]
Participants will continue treatment with study medication until disease progression, unmanageable toxicity, criteria for discontinuation are met, or withdrawal of consent.

Where possible, participants will attend an SFU Visit approximately 30 days after discontinuation of study treatment and a Final Visit approximately 3 months after discontinuation of study treatment. The Final Visit may be undertaken by phone, where applicable.

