### 7.1.3 Other criteria for discontinuation of study medication

Participants must discontinue study treatment if they experience any of the following:

1. There is confirmation of a pregnancy during the study, as evidenced by a positive pregnancy test.
2. The participant experiences unacceptable toxicity.
  - For information on dose delays due to drug-related toxicity, see Section [6.6.1](#) (Part A and Part A1), Section [6.6.2](#) (Part B), and Section [6.6.3](#) (Part C). Participants will discontinue treatment, unless, in the opinion of the investigator, they are experiencing clinical benefit and it is in their best interest to continue treatment. For these participants, treatment may continue at a reduced dose at the discretion of the investigator and Sponsor.
3. The participant has documented evidence of progressive disease.
  - Participants with progressive disease before the end of Cycle 1 may be discontinued from study medication at the discretion of the investigator. Participants with progressive disease beyond Cycle 1 will be discontinued from study medication. In cases where progression is not clear and, in the opinion of the investigator, the participant may be having clinical benefit, the participant may continue treatment, but must be reimaged within 2 cycles of treatment.
4. The participant, for any reason, requires treatment with another therapeutic agent or modality for his/her cancer (with the exception of palliative bone-directed radiotherapy). In this case, discontinuation from the study treatment must occur before introduction of the new agent or modality.

---

5. Participant takes prohibited concomitant medications as defined in this protocol.

Participants who discontinue the study medication and/or study early will have end-of-study (SFU) procedures performed as shown in the Schedules of Activities for Part A ([Table 1-4](#)), Part A1 ([Table 1-5](#) and [Table 1-6](#)), Part B ([Table 1-7](#)), and Part C ([Table 1-8](#)).

See the Schedules of Activities for Part A ([Table 1-4](#)), Part A1 ([Table 1-5 and Table 1-6](#)), Part B ([Table 1-7](#)), and Part C ([Table 1-8](#)) for data to be collected at the time of study treatment discontinuation and follow-up and for any further evaluations that need to be completed.

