### **9.1.6        Pregnancy testing**

Procedures for pregnancy testing and contraceptive use are provided in Appendix 4 (Section 11.4). Pregnancy testing should be collected as described in the Schedules of Activities for Part A (Table 1-4), Part A1 (Table 1-5 and Table 1-6), Part B (Table 1-7), and Part C (Table 1-8).

For female participants of childbearing potential, a serum pregnancy test with sensitivity of at least 25mIU/mL will be performed on 2 occasions prior to starting study therapy, as follows: once at the start of Screening and once at the Day 1 Cycle 1 visit immediately before the investigational product administration.

Following a negative pregnancy test result at Screening, appropriate contraception must be commenced, and another negative pregnancy test result will then be required at the Day 1 Cycle 1 Visit before the participant may receive the study treatment.

Serum or urine pregnancy tests will also be routinely repeated twice at every treatment cycle during the active Treatment Period, at the Final Visit, and additionally whenever 1 menstrual cycle is missed or when potential pregnancy is otherwise suspected. In the case of a positive pregnancy test, the participant will be withdrawn from treatment but may remain in the study (Section 9.2.5).

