#### **9.2.5 Pregnancy**

Details of all pregnancies in female participants and female partners of male participants will be collected after the start of study treatment and until 3 months after the last study treatment administration.

If a pregnancy is reported, the investigator must immediately inform the Sponsor within 24 hours of learning of the pregnancy and should follow the procedures outlined in Appendix 4 (Section 11.4).

Female participants should be withdrawn from the study as soon as pregnancy is known (by positive pregnancy test), and the following should be completed:

- The participant should return for a Safety Follow-up Visit.
- The participant should immediately stop the intake of the study medication or be down-titrated as instructed at the Safety Follow-up Visit.
- A Final Visit should be scheduled 3 months after the participant has discontinued her study medication.

Abnormal pregnancy outcomes (eg, spontaneous abortion, fetal death, stillbirth, congenital anomalies, ectopic pregnancy) are considered SAEs.

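### Appendix 4 lets a participant who becomes pregnant ask to stay on study medication, and Section 9.2.5 offers down-titration, although Sections 7.1.3 and 9.1.6 require treatment to stop

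*Protocol*

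**What the plan says.** Four places in the protocol deal with a positive pregnancy test during treatment.

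- **Section 7.1.3** opens with "Participants must discontinue study treatment if they experience any of the following", and its first item reads "There is confirmation of a pregnancy during the study, as evidenced by a positive pregnancy test". That item has no exception. Allowances for a participant who is benefiting appear only under item 2 (toxicity) and item 3 (progression).
- **Section 9.1.6** says that "the participant will be withdrawn from treatment but may remain in the study", and points to Section 9.2.5.
- **Section 9.2.5** requires the investigator to inform the Sponsor within 24 hours and says the investigator "should follow the procedures outlined in Appendix 4 (Section 11.4"). On study status it says "Female participants should be withdrawn from the study as soon as pregnancy is known (by positive pregnancy test"). On medication it says "The participant should immediately stop the intake of the study medication or be down-titrated as instructed at the Safety Follow-up Visit".
- **Appendix 4 (Section 11.4)**, on female participants who become pregnant, says that she "will discontinue study medication or be withdrawn from the study OR may request continuation of study medication".

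**The concern.** A site that starts at Section 9.1.6 and follows the cross-references through Section 9.2.5 arrives at Appendix 4. There, continued dosing stands as an alternative to stopping, contrary to Section 7.1.3. The capitalised OR sets the request beside both discontinuation and withdrawal.

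The protocol itself shows why fetal exposure matters. Section 2.2 describes gremlin-1, the target that UCB6114 neutralizes, as essential to skeletal and kidney development. It also reports mechanism-related ovarian changes in female rats. The nonclinical safety program is summarized there as two 13-week repeat-dose studies, and no embryofetal study is mentioned. Part B adds TFD/TPI and Part C adds mFOLFOX6. The entry criteria exclude pregnancy and require contraception for at least 3 months (Parts A and A1) or 6 months (Parts B and C) after the final dose. Pregnancy testing during treatment loses much of its purpose if a positive result need not stop dosing.

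**Working it through.** The plan states no figure to reproduce on this point, so the check is a comparison of texts.

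**1. Side by side**

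| Section | Study medication | Study participation |
|---|---|---|
| 7.1.3 | Must stop; no exception on the pregnancy item | Not addressed |
| 9.1.6 | Withdrawn from treatment | May remain |
| 9.2.5 | Stop, or be down-titrated | Should be withdrawn |
| Appendix 4 | Discontinue, or may request continuation | Withdrawal is one of the options |

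Two sections require a stop. Two offer something other than a stop, although Section 9.2.5 also directs withdrawal from the study. No clause ranks the sections.

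**2. Is the continuation option a controlled exception?** Where Section 7.1.3 allows treatment to continue at a reduced dose after toxicity, it names who decides: the investigator and the Sponsor. Appendix 4 names no decider and no grounds. Section 9 rules out protocol waivers, so a granted request could not be handled as a waiver of Section 7.1.3 either.

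**3. Can the down-titration option be carried out?** It is to be instructed at the Safety Follow-up (SFU) Visit.

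- Under Treatment groups and duration in the synopsis, "participants will attend an SFU Visit approximately 30 days after discontinuation of study treatment". The Schedules of Activities place the visit within 30 days after the last dose. On either wording it is timed from the end of dosing, so a dose reduction cannot sensibly begin there.
- Section 6.6.1.3 rules out any dose adjustment in Part A1.
- Section 6.6.1.2 ties Part A adjustments to dose-limiting toxicity.
- Sections 6.6.2.3 and 6.6.3.4 tie reductions of TFD/TPI and mFOLFOX6 to adverse events related to those drugs.
- No section describes a taper for pregnancy.

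**4. Size of the exposure if one more 28-day cycle were given**

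- UCB6114 in Parts B and C: Days 1 and 15 = 2 infusions.
- TFD/TPI in Part B: Days 1 to 5 and 8 to 12 = 5 + 5 = 10 days; 10 days × 2 doses per day = 20 doses.
- mFOLFOX6 in Part C: started on Days 1 and 15 = 2 administrations.

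These counts only restate the schedule for each extra cycle. They do not estimate how often the event would occur.

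**5. Study status.** The three wordings differ, but little depends on that. The SFU Visit, the Final Visit and the survival check are kept after withdrawal unless she withdraws consent (Sections 7.2 and 10.4.1.1). Pregnancy-outcome follow-up is kept under Appendix 4.

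**The case against.** The strongest case on the other side is that continued dosing is blocked several times over. Section 9.2.5 directs withdrawal from the study once pregnancy is known and sets the Final Visit 3 months after medication has been discontinued, so it presupposes a stop. Section 7.1 says the drug is discontinued when a stopping criterion is met, and Section 9 allows no waivers. The Sponsor hears of the pregnancy within 24 hours, so dosing would not continue unnoticed. A right to request is not a right to receive. The reference to Appendix 4 in Section 9.2.5 sits in the sentence on notifying the Sponsor, and can be read as covering reporting only. Down-titration can be read as a taper to a stop, and if it is unworkable it opens no real route to exposure.

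Much of this is fair. It makes prolonged dosing of a pregnant participant unlikely, and it makes down-titration the weaker of the two limbs. The count of two sections against two also carries little weight, because Section 9.2.5 points both ways. But each of these bars is one more statement that Appendix 4 contradicts, and none says which text prevails. Under a rule that she must discontinue there is nothing to request, yet Appendix 4 presents the request as an alternative to discontinuing. A restricted reading of the cross-reference does not help a site that opens Appendix 4, because the medication instruction is there under its own heading.

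**Conclusion.** The concern holds. The protocol contradicts itself on whether a pregnant participant may continue study medication. This is an internal contradiction affecting participant safety, and it should be corrected. The continuation option in Appendix 4 is the main defect. The down-titration option in Section 9.2.5 is secondary, and the differing wording on study status is minor.

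The conclusion rests on the current Amendment 6 text as written and on finding no precedence clause in the protocol. Events should be rare given the contraception and testing requirements. The protocol does not give the number of women of childbearing potential, so no count of affected participants is claimed. No endpoint, estimate or escalation rule changes. The case for correction is the seriousness of a single exposure in a first-in-human study that includes cytotoxic combinations, set against a remedy that needs wording only.

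**What to change.** 1. Keep the mandatory stop in Sections 7.1.3 and 9.1.6 unchanged, applying to all study medication.
2. In Appendix 4, delete the final alternative, from the capitalised OR to the end of the sentence.
3. In Section 9.2.5, delete the down-titration alternative together with its reference to the Safety Follow-up Visit, leaving the immediate stop.
4. Use one sentence in Sections 9.1.6, 9.2.5 and Appendix 4, for example: *A participant with a positive pregnancy test stops all study medication at once and, with her consent, completes the Safety Follow-up Visit, the Final Visit and the pregnancy-outcome follow-up.*

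The cost is two deletions and one aligned sentence in an amendment, with the IRB/IEC approval that Section 11.1.1 requires for changes. Visits, data collection and analysis stay as they are.
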